- Process for Aim #3: Patients with ARDS will be analyzed based on hypoxemia conditions (as defined by their PaO₂ to FiO₂ ratio) using 3 classifications: mild (201-300), moderate (101-200), and severe (≤100). This subgroup analysis will evaluate protocol implementation of the high versus low positive end expiratory pressure (PEEP) protocol and assess relationship with patient outcomes. Data from Intermountain ICUs in 2014 have shown that approximately 500 patients meet the criteria for "severe" hypoxemia. Patients with moderate and severe hypoxemia will be identified to determine the frequency of high PEEP protocol usage (which is the recommendation in the protocol). Implementation of the high PEEP protocol will be based upon clinician discretion. We will assess outcomes in the 4 hypoxemia sub-groups noted above using a stratified Kaplan–Meier curve to determine differences in mortality using log rank statistics.
- Hypothesis 3: A high PEEP strategy in patients with moderate to severe hypoxemia and ARDS will improve outcomes.

Specific Aim #4: Measure compliance of the computerized lung protective ventilation protocol after implementation across Intermountain Healthcare's 11

hospitals that manage mechanically ventilated patients with acute respiratory failure.

- Process for Aim #4: Tool utilization and compliance will test the ability
 of a healthcare system to introduce this proven lung protective
 ventilation protocol in a new electronic medical record in a controlled
 clinical environment. To ensure that this is successful, [name] will
 identify local champions to train and educate the healthcare providers.
- Hypothesis 4: Healthcare providers will utilize the computerized ventilation protocol and will comply with protocol instructions.

Study Design:

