Note that although 11 hospitals will be included in the study (IMC, McKay-Dee, Utah Valley, American Fork, Dixie, Valley View, LDS, Riverton), only eight were included in the power analysis because three hospitals (Alta View, Park City, and Logan) were not featured in the baseline data set. The number of mechanically ventilated patients at Alta View, Park City, and Logan is very low, so their expected contribution to patient enrollment would not substantively change the results of the power analysis. These three hospitals will be included in the prospective implementation of a lung protective ventilation protocol for purposes of standardization of care. Critically ill patients with respiratory failure who are intubated at Alta View, Park City, and Logan may have initiation of lung protective mechanical ventilation for management in their ICU, or prior to transfer to an Intermountain tertiary hospital. With a two-month deployment period at each hospital – during which time data will not be collected – a sufficient number of patients could be enrolled in less than 16 months. This corresponds to two months of baseline data collection, eight months of phasing in the protocol, and six months of follow-up once the protocol has been successfully implemented at each of the sites. An example enrollment matrix simulated by a Poisson process is displayed in **Table 5**.

Table 5. 16-month enrollment matrix (n = 4,127)

	NOV	DEC	JAN	FEB	MAR	APR	MAY	JUN	JUL	AUG	SEP	ОСТ	NOV	DEC	JAN	FEB
McKay-Dee	46	39			50	43	55	37	49	50	39	42	52	49	43	61
Utah Valley	52	60	57	57			54	45	72	38	57	54	46	60	48	49
American Fork	8	4	6	10			6	5	4	4	5	6	2	3	10	3
Dixie	45	43	37	34	31	52			33	38	41	43	37	36	47	52
Valley View	3	4	5	6	7	2			7	5	3	4	8	1	5	3
IMC	129	127	116	105	114	130	136	142			115	121	139	120	116	118
LDS	19	19	16	24	17	23	19	12			10	18	17	9	15	15
Riverton	3	3	5	3	1	5	4	5			2	6	7	5	4	1

Risks

The risk of this study is a potential loss of confidentiality, which will be managed as detailed below.

Benefits

This is a quality improvement study evaluating the benefits of a proven lung protective ventilation protocol across Intermountain Healthcare hospitals. Application of the protocol at the discretion of the attending physician to patients with acute respiratory failure requiring intubation and mechanical ventilation is expected to improve outcomes.

Waiver of Informed Consent

This study seeks a waiver of informed consent for these reasons:

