- The risk of this study is a potential loss of confidentiality. The study involves no more than minimal risk to the subject, as the study is observational only and the study will not alter the care that enrolled subjects receive. The computerized lung protective mechanical ventilation protocol will be available to clinicians as an order in iCentra, but will not be required.
- The sample size required to detect a significant change in VFD is estimated to be about 3,900 subjects. Including only the data for which consent can be obtained would prevent accurate conclusions from being drawn.
 Consequently, the research could not practicably be carried out without a waiver of consent.

Waiver of Authorization

PHI will be collected as a part of this study. The PHI will be used only for study purposes and will not be reused or disclosed except as required by law. The information obtained from medical records will be kept separate from clinical records.

All digital study records will be kept within the Intermountain Healthcare firewall in a location that is only accessible to authorized members of the study team. All paper study records will be maintained on a floor with secure badge access that only the research team can access.

After the study is complete, study identifiers will be removed from the dataset.

The data to be collected is detailed below. In particular, the dates to be collected are important for evaluating the primary outcome of interest, VFDs to 28 days.

Data Collection:

Data Elements Extracted from the EDW for the Mechanical Ventilation Study

- Region
- Hospital
- Facility ID
- Account Number
- EMPI
- Admit Date
- Discharge Date
- Admit Year
- Age
- Gender
- ICD Diagnosis code
- ICD Diagnosis description
- ICD Diagnosis long description
- ICU Stay
- Length of Stay(Days)
- Mortality Indicator
- Patient Type(inpatient(I) vs outpatient(O))
- Patient Type(Detailed code)
- Patient Type Description
- Death Location
- Discharge Disposition Description
- Discharge Reason(same as above)
- ED Admit Date
- ED Discharge Date
- Total Cost
- Ventilator Location(First Vent Check Location)
- First Date of Ventilator Check
- Ventilator Mode
- First Date of Ventilator Check
- Intubation Date
- Intubation Location(Same as Ventilator Location)
- Room Trace(It is more detailed than the ones above)
- In Hospital Mortality

- Ventilator Mode
- Machine Corrected Volume
- Set Tidal Volume
- Spontaneous Volume
- Height
- Predicted Body Weight

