Generalized linear mixed models (GLMM) with hospital-level random intercepts and an identify link function will be used to measure the effect of initial tidal volume size on VFD. It is proposed to measure the treatment as a continuous variable (rather than as a dichotomous indicator of whether the mechanically ventilated patient was cared for at a post-intervention site) in order to account for the variable "usual care" practices of tidal volume size. The protocol will be phased sequentially in a non-randomized phased implementation manner. Since it is hypothesized that the bundle will improve care and, resultantly, decrease duration of time on ventilator, statistical significance will be determined by a one-tailed, 5% significance test. Heterogeneity among clusters will also be measured and accounted for random intercepts. Potential secular trends will be adjusted for by inclusion of quadratic time effects, which would capture a variety of time effects – from linear to bell-shaped. Patient-specific confounders will be controlled for by additive inclusion of a matrix of patient-level covariates.

Mitigation Plans and Interim Analysis

We plan an interim analysis for futility and efficacy at the end of the third step, following the successful phasing in of the second cluster. If the mean VFD following implementation of the bundle is equivalent to the mean VFD prior to implementation (according to the two one-sided test procedure with 99% confidence having an equivalence margin of four hours) then futility will be declared and further data collection will cease. Conversely, if the mean VFD following implementation has increased by more than 2 days (according to a one-sided hypothesis test with 99% confidence), efficacy will have been established and further data collection will also cease.

Data Sharing:

Development of the ventilation protocol in iCentra for mechanical ventilation will likely increase the number of VFDs, decrease healthcare utilization and decrease cost. To ensure that the proposal deliverables are met, we have designed the following dissemination plan:

Internal Strategic Planning

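### The interim rule would end all data collection when only one to three hospitals have post-implementation patients, on a contrast whose hospital adjustment is not stated

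*Protocol*

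**What the plan says.** The section on mitigation plans and interim analysis states: "We plan an interim analysis for futility and efficacy at the end of the third step, following the successful phasing in of the second cluster". Futility is declared if the mean VFD after implementation is equivalent to the mean before it, by two one-sided tests at 99% confidence with a four-hour margin. Efficacy is declared "if the mean VFD following implementation has increased by more than 2 days", "according to a one-sided hypothesis test with 99% confidence". In that case "efficacy will have been established and further data collection will also cease". Futility ends collection too. Neither sentence exempts any hospital, aim or outcome.

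The Data Analysis section gives the main model hospital random intercepts, quadratic time effects and patient covariates, and calls the roll-out non-randomised. The interim rule mentions none of these terms.

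Specific Aim #4 is to "Measure compliance of the computerized lung protective ventilation protocol after implementation" across 11 hospitals. The waiver-of-consent section says: "The computerized lung protective mechanical ventilation protocol will be available to clinicians as an order in iCentra, but will not be required".

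**The concern.** The look comes early in a staggered roll-out, when most hospitals have not yet switched. If the rule fires, they never supply a post-implementation patient. Aim 4 then cannot be answered for most of the system, and post-implementation data for the ARDS and high-PEEP aims and for the secondary outcomes are cut sharply.

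The contrast that triggers the stop is worded as one overall mean against another. Early in the roll-out, the post group comes from the first hospitals to switch and the pre group mostly from hospitals still waiting. Lasting differences between hospitals in case mix or practice can then look like an effect of the protocol.

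**Working it through.** **Inputs.** Monthly counts and washout gaps from Table 5; 2014 volumes from Table 4; SD 7.8 and ICC 0.10 from the Sample Size section, with ICC 0.01 and 0.20 from Table 3; the 2-day threshold, the four-hour margin and the 99% level from the interim section.

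**1. Reproducing Table 5.** The row sums are 655 + 749 + 76 + 569 + 63 + 1,728 + 233 + 54 = 4,127, the stated total. The washout order is McKay-Dee; then Utah Valley and American Fork; then Dixie and Valley View; then IMC, LDS and Riverton.

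**2. Who has post-implementation data at the look.** The third step can be read in two ways.

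| | Baseline counted as step 1 (end April) | Baseline not counted (end June) |
|---|---|---|
| Post | 50 + 43 = 93, McKay-Dee only | 185 + 99 + 11 = 295, three hospitals |
| Pre | 1,467 | 1,785 |
| Switched hospitals' share of pre | 85/1,467 = 6% | 339/1,785 = 19% |
| IMC share of pre | 721/1,467 = 49% | 999/1,785 = 56% |

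**3. Volume with no post-implementation data after a stop.** Table 4 sums to 3,421. In June, Dixie, Valley View, IMC, LDS and Riverton have none: (479 + 60 + 1,409 + 206 + 49)/3,421 = 2,203/3,421 = 64%. In April, Utah Valley and American Fork are added: (2,203 + 608 + 68)/3,421 = 84%. Collecting to the planned end of Table 5 gives 4,127 − 1,785 = 2,342 post-implementation patients from all eight scheduled hospitals, so the look has 4% (93) or 13% (295) of them.

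**4. The pooled contrast with no true effect, ICC 0.10.** SD 7.8 is taken as the total SD, with normal hospital intercepts.
- Between-hospital SD = √0.10 × 7.8 = 2.47 days.
- With c_j = hospital j's share of the post group minus its share of the pre group, Σc_j² = 1.187 (April) or 0.719 (June). The hospital mix alone therefore gives the contrast an SD of 2.47 × √1.187 = 2.69 or 2.47 × √0.719 = 2.09 days.
- Sampling SD = √0.90 × 7.8 × √(1/n_pre + 1/n_post) = 0.79 or 0.47. The total SD is 2.80 or 2.14.
- Naive SE, treating patients as independent: 7.8 × √(1/1,467 + 1/93) = 0.834, or 7.8 × √(1/1,785 + 1/295) = 0.490.
- Observed gain needed to show more than 2 days: 2 + 2.326 × SE = 3.94 or 3.14 days.
- Chance of a false efficacy stop: 1 − Φ(3.94/2.80) = 8.0%, or 1 − Φ(3.14/2.14) = 7.1%.

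**5. How this depends on the ICC and the standard error.**

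| Test against 2 days, no true effect | April | June |
|---|---|---|
| Naive SE, ICC 0.01 | about 0.05% | under 0.01% |
| Naive SE, ICC 0.10 | 8.0% | 7.1% |
| Naive SE, ICC 0.20 | 15.5% | 14.7% |
| Same contrast, SE including hospital variance, ICC 0.10 | 0.12% | 0.06% |
| Within switched hospitals | under 0.01% | under 0.01% |

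In April the within-hospital contrast is McKay-Dee alone, 85 pre against 93 post, with SE 7.8 × √(1/85 + 1/93) = 1.17.

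**6. What would trigger a stop.** With no hospital differences and a true gain of 1.5 days (the design effect), the naive test against 2 days stops in only 0.18% (April) or 0.04% (June) of cases. A stop from the pooled test would therefore come mostly from hospital mix.

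**7. The futility sentence.** With the naive SE, the 99% half-width is 2.326 × 0.834 = 1.94 or 2.326 × 0.490 = 1.14 days, against a margin of 4/24 = 0.167 day. Equivalence could hardly be declared at this look, but the sentence has the same consequence if it were.

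**The case against.** The strongest reply is that the protocol does not fix the interim estimator. The main model carries hospital intercepts and time terms, and the analysis plan may apply it at the interim; the rule would then almost never fire. This stands: the 7% to 8% is conditional on a naive pooled test, which the wording suggests but does not prescribe. It does not answer the loss of data, because no model replaces patients who were never collected.

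Three stronger readings are tempting.
- A reader might infer false-stop rates of 24% (April) or 17% to 18% (June), by requiring an observed gain above 2 days that is significant against zero. The text ties the 99% test to a gain of more than 2 days, so that reading is less literal.
- A reader might infer that the rule compares entirely different hospitals. It does not: the pre group includes the switched hospitals' own baseline, 6% to 19% of it. The fault is an unequal mix with no stated adjustment.
- A reader might infer that Aims 2 and 3 would rest on one to three hospitals. The main analysis uses initial tidal volume as a continuous exposure, so pre-implementation patients at every hospital contribute. What is lost is most of the post-implementation data.

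Two further points are fair. Table 5 is a simulated example that omits three hospitals, which the protocol describes as very low in volume. Stopping would also limit the handling of protected health information, and loss of confidentiality is the one study risk named. Neither removes the problem. The Study Design section says each successive hospital will be followed, but the stopping sentences make no exception for this.

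**Conclusion.** The concern holds. The protocol itself fixes the timing, threshold and consequence of the look, so this is not a detail left to an analysis plan. If the rule fires, hospitals with 64% to 84% of the volume, IMC included, have no post-implementation data, and Aim 4 cannot be answered for most of the system. This conclusion rests on the Table 5 roll-out order and does not depend on the ICC or the test used. No patient is spared an exposure in return, since use of the order is voluntary and the roll-out proceeds regardless.

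The second part is conditional. A naive pooled test against 2 days at SD 7.8 and ICC 0.10 gives a false efficacy stop of about 7% to 8% against a nominal 1%. The range is from about 0.05% or less at ICC 0.01 to about 15% at ICC 0.20. A cluster-aware or within-hospital test brings it to about 0.1% or less at ICC 0.10. The documents do not show that the rule is bound to fire or that the naive test is the one intended.

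**What to change.** Remove the end of data collection from both the efficacy and the futility sentences, and state that extraction continues at all hospitals to the planned end. If an interim efficacy test is kept, specify that it uses the main model, with hospital and calendar-time terms and a within-hospital before/after contrast, and not pooled means. Ideally hold it once all clusters have post-implementation patients, and state which calendar point the third step denotes.

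The edit is a few sentences. The running cost is data extraction for the remaining months, which includes chest-radiograph review to identify ARDS and continued handling of protected health information. The study also gives up an early stop for efficacy or futility.

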Figure 3. Initial Tidal Volume on Initiation of Mechanical Ventilation at Intermountain Healthcare Hospitals (Intermountain Medical Center = IMC, Utah Valley = UV, McKay Dee = MK, Dixie = DX, and LD = LDS Hospital).

[figure not shown]

Figure 4: An example of the weaning protocol that will be used in this study.

[figure not shown]
[figure not shown]

Figure 5: Process Flow Map for Supporting the Weaning Protocol

Rules for I Centra Ventilator Protocol

efi.			

- □ BWP: Body weight predicted (formula below)
 - \circ Males: PBW (kg) = 50 + 2.3[height (inches) -60]
 - \circ Females: PBW (kg = 45.5 + 2.3 [height (inches) -60]
- □ ABG: arterial blood gas
- □ VR: respiratory rate (breaths per minute)
- □ VT: tidal volume (milliliters)
- □ VE: minute volume (liters per minute)
- □ CMV: continuous mandatory ventilation
- □ VC: Volume Control
- □ PEEP: positive end expiratory pressure (cmH2O)
- ☐ Measured Pplat: actual measured plateau pressure

General:

- ☐ If the PBW does not appear or is too small or too large, check the height and gender in the computer they could be entered wrong or not at all.
- ☐ The protocol will not generate new instructions if it has been 2 or more hours since a complete ventilator assessment has been entered.
- □ Always do a ventilator assessment before drawing an ABG.
- ☐ Check for typos. The computer relies on accurate and timely charting.
- ☐ The protocol will run off arterial blood gas or oxygen saturation measured by the pulse oximeter.
- □ Protocol suspensions can be entered proactively or retroactively.
- □ Suspend the protocol when the patient will be receiving a procedure, traveling, going to surgery or hyperbaric.
- ☐ Unsuspend the protocol when back in the unit
- ☐ Enter at the previous settings
- ☐ Enter at the current settings charted (patient may have different needs after the procedure)
- The protocols are orders. Deviation from the protocol requires a physician order.

ABG Recommended For:

□ Change in Mode.

ABG Required For:

- □ 10% change in VT setting.
- □ Change in VR setting if patient is not assisting.
- Receive ventilation protocol instructions.

Ventilation:

- ☐ The low range for the set ventilatory rate is 6 breaths per minute for all protocols.
- □ Ventilation instructions are only given after an ABG.
- ☐ The protocol will set a back up VR if the patient is breathing over the set rate. Backup VR is based on a calculated VE goal.
- □ Set VT at 6ml/kg PWB
- □ VE goal = Current VE *(PaCO2/50 * HCO3-/24)

☐ Entry criteria for weaning:

□ Without neuromuscular blockade

□ Weaning assessment will be attempted every 4 hours.

 \Box Peep < = 10 cmH2O

 \Box Total VR > set VR

 \Box FiO2 < = .5

	Backup set $VR = VE$ goal / set VT
	Volume control ventilation will be required unless FiO2 <= 0.5 and PEEP <= 10cmH2O, then the
	patient can be evaluated for pressure support weaning.
	Tidal Volume (VT) Goal is 6 ml / kg / PBW
	Measure and record inspiratory plateau pressure (Pplat) with every ventilator assessment and after
	changes in VT and PEEP.
	If Pplat is > 30 cmH2O an ABG is recommended to determine if a VT reduction is indicated.
	If unable to measure a Pplat when in PRVC, change the mode to A/C for 2 to 3 minutes. Measure the
	Pplat. Return the patient to previous mode.
	Do not increase ventilator rate (VR) above 35 bpm.
	Do not decrease VT below 4 ml/kg
	If the patient is not over breathing the set rate do not decrease VT and VR at the same time.
Oxy	ygenation:
	The protocol will not decrease PEEP for 6 hours after it has been increased.
	If PEEP is > 10 cmH2O, do not decrease > 2cmH2O every 2 hours.
	If the SpO2 or PaO2 fall below the target ranges after a decrease in FiO2 and/or PEEP and it has been
	less than 30 minutes, the patient will be returned to the previous FiO2 and PEEP settings.
	Each subsequent repeat of therapy reduction followed by therapy increase will result in waiting periods
	(4, 8, and 24 hours).
Nig	tht time:
	Night rests on CMV will start at 22:00 and end at 06:00 when ordered.
We	aning:
	Weaning may occur 24 hours a day.
	Weaning may be initiated at any time.

Table B.1. Tidal Volumes from Predicted Body Weight from Height and Gender

HEIG	ΗΤ	PBW	4 mi	5 m i	6 m l	7 m l	8 mi
4' 0" (4	48)	17.9	72	90	107	125	143
4' 1" (4	49)	20.2	81	101	121	141	162
4' 2" (50)	22.5	90	113	135	158	180
4' 3" (51)	24.8	99	124	149	174	198
4' 4" (52)	27.1	108	136	163	190	217
	53)	29.4	118	147	176	206	235
4' 6" (54)	31.7	127	159	190	222	254
4' 7" (55)	34	136	170	204	238	272
4' 8" (56)	36.3	145	182	218	254	290
4' 9" (57)	38.6	154	193	232	270	309
4' 10" (58)	40.9	164	205	245	286	327
4' 11" (59)	43.2	173	216	259	302	346
	60)	45.5	182	228	273	319	364
5' 1" (0	61)	47.8	191	239	287	335	382
5' 2" (0	62)	50.1	200	251	301	351	401
5' 3" (63)	52.4	210	262	314	367	419
	64)	54.7	219	274	328	383	438
	65)	57	228	285	342	399	456
5' 6" (6	66)	59.3	237	297	356	415	474
5' 7" (67)	61.6	246	308	370	431	493
5' 8" (6	68)	63.9	256	320	383	447	511
5' 9" (69)	66.2	265	331	397	463	530
	70)	68.5	274	343	411	480	548
	71)	70.8	283	354	425	496	566
	72)	73.1	292	366	439	512	585
	73)	75.4	302	377	452	528	603
	74)	77.7	311	389	466	544	622
	75)	80	320	400	480	560	640
	76)	82.3	329	412	494	576	658
	77)	84.6	338	423	508	592	677
	78)	86.9	348	435	521	608	695
	79)	89.2	357	446	535	624	714
	80)	91.5	366	458	549	641	732
	81)	93.8	375	469	563	657	750
	82)	96.1	384	481	577	673	769
	83)	98.4	394	492	590	689	787
7' 0" (8	84)	100.7	403	504	604	705	806

HEIGHT	PBW	4 mi	5 ml	6 mi	7 ml	8 ml
4' 0" (48)	22.4	90	112	134	157	179
4' 1" (49)	24.7	99	124	148	173	198
4' 2" (50)	27	108	135	162	189	216
4' 3" (51)	29.3	117	147	176	205	234
4' 4" (52)	31.6	126	158	190	221	253
4' 5" (53)	33.9		170			
4' 6" (54)	36.2			217		
4' 7" (55)		104	193		270	
4' 8" (56)	40.8		204		286	
4' 9" (57)	43.1		216			
4' 10" (58)	45.4		227		318	
4' 11" (59)	47.7		239		334	
5' 0" (60)	50	200	250	300	350	400
5' 1" (61)	52.3	209	262	314	366	418
5' 2" (62)	54.6	218	273	328	382	437
5' 3" (63)	56.9	228	285	341	398	455
5' 4" (64)	59.2	237	296	355	414	474
5' 5" (65)	61.5	246	308	369	431	492
5' 6" (66)	63.8	255	319	383	447	510
5' 7" (67)	66.1		331			529
5' 8" (68)	68.4	274	342	410	479	547
5' 9" (69)		283	354			
5' 10" (70)	73	292	365	438	511	584
5' 11" (71)	75.3		377		527	
6' 0" (72)		310	388			621
6' 1" (73)		020		479		
6' 2" (74)		329				
6' 3" (75)		338		507	592	
6' 4" (76)		347			608	
6' 5" (77)		356	446			
6' 6" (78)	91.4		457		640	731
6' 7" (79)	93.7	375	469		656	750
6' 8" (80)	96	384	480	576	672	768
6' 9" (81)	98.3				688	786
6' 10" (82)	100.6	402	503	604	704	805
6' 11" (83)	102.9					823
7' 0" (84)	105.2	421	526	631	736	842

PBW and Tidal Volume for Females

PBW and Tidal Volume for Males

Table B.2.	1.	VT > 6 ml/	/kg	2.	VT = 6 ml/k	kg .	VT ≥ 4	ml/kg and < 6 ml/l	kg
рН	3. Pplat < 25 cm H2O	Pplat 25 – 30 cm H2O	4. Pplat > 30 cm H2O	5. Pplat < 25 cm H2O	Pplat 25 – 30 cm H2O	Pplat > 30 cm H2O	6. Pplat < 25 cm H2O	Pplat 25 – 30 cm H2O	Pplat > 30 cm H2O
> 7.45	1. ↓ VT by 1 ml/kg	2. ↓ VT by 1 ml/kg	3. ↓ VT by 1 ml/kg	4. ↓ VR by 20%	5. ↓ VR by 20%	6. ↓VT by 1 ml/kg	7. ↑ VT by 1 ml/kg ↓ VR by 20%	8. ↓ VR by 20%	9. ↓ VT by 1 ml/kg but do not ↓ < 4 ml/kg
7.30 – 7.45	10. ↓ VT by 1 ml/kg	11. ↓ VT by 1 ml/kg	12. ↓ VT by 1 ml/kg	13. No Change in Therapy	14. No Change in Therapy	15. ↓ VT by 1 ml/kg	16. ↑ VT by 1 ml/kg	17. No Change in Therapy	18. ↓ VT by 1 ml/kg but do not ↓ < 4 ml/kg
7.15 – 7.29 and VR < 35 bpm (measured rate)	19. ↑ VR by 20% increments ^a ↓ VT by 1 ml/kg	20. ↑ VR by 20% increments ^a ↓ VT by 1 ml/kg	21. ↑ VR by 20% increments ^a ↓ VT by 1 ml/kg	22. ↑ VR by 20% increments ^a	23. ↑ VR by 20% increments ^a	24. ↓ VT by 1 ml/kg ↑ VR by 20% increments ^a	25. ↑ VR by 20% increments ^a ↑ VT by 1 ml/kg	26. ↑ VR by 20% increments ^a	27. ↑ VR by 20% increments ^a
7.15 – 7.29 and VR = 35 bpm (measured rate)	28. ↓ VT by 1 ml/kg Check with MD to consider Bicarb	29. ↓ VT by 1 ml/kg Check with MD to consider Bicarb	30. ↓ VT by 1 ml/kg Check with MD to consider Bicarb	31. Check with MD to consider Bicarb	32. Check with MD to consider Bicarb	33. ↓ VT by 1 ml/kg Check with MD to consider Bicarb	34. ↑ VT by 1 ml/kg Check with MD to consider Bicarb	35. Check with MD to consider Bicarb	36. ↓ VT by 1 ml/kg but do not ↓ < 4 ml/kg Check with MD To consider Bicarb
< 7.15 and VR < 35 bpm (measured rate)	37. ↑ VR by 20% increments Check with MD to consider Bicarb	38. ↑ VR by 20% increments Check with MD to Consider Bicarb	39. ↑ VR by 20% increments Check with MD to Consider Bicarb	40. ↑ VR by 20% increments Check with MD to Consider Bicarb	41. ↑VR by 20% increments Check with MD to Consider Bicarb	42. ↓ VT by 1 ml/kg Check with MD to consider Bicarb	43. ↑ VR by 20% increments ^a ↑ VT by 1 ml/kg Check with MD to consider Bicarb	44. ↑ VR by 20% increments Check with MD to Consider Bicarb	45. ↑ VR by 20% increments Check with MD to Consider Bicarb
< 7.15 and VR = 35 bpm (measured rate)	46. Check with MD to consider Bicarb prior to ↑ VT by 1 ml/kg	47. Check with MD to consider Bicarb prior to ↑ VT by 1 ml/kg	48. Check with MD to consider Bicarb prior to ↑ VT by 1 ml/kg	49. Check with MD to consider Bicarb prior to ↑ VT by 1 ml/kg	50. Check with MD to consider Bicarb prior to ↑ VT by 1 ml/kg	51. Check with MD to consider Bicarb prior to ↑ VT by 1 ml/kg		53. Check with MD to consider Bicarb prior to ↑ VT by 1 ml/kg	54. Check with MD to consider Bicarb prior to ↑ VT by 1 ml/kg

$PaO_2 < 50 \text{ or } SpO_2 < 85\%$

(Use PaO₂ if available, only use SpO₂ if PaO₂ not available)

When PaO_2 or SpO_2 are in this low range, repeated sequential adjustments may be made as guided by the cells in the table until adequate oxygenation with a $SpO_2 \ge 88\%$ is achieved

PEEP	FiO ₂ = .3	$FiO_2 = .4$	FiO ₂ = .5	$FiO_2 = .6$	$FiO_2 = .7$	$FiO_2 = .8$	FiO ₂ = .9	$FiO_2 = 1.0$
24	↑ FiO ₂ 0.3	↑ FiO ₂ 0.3	↑ FiO ₂ 0.3	↑ FiO ₂ 0.3	↑ FiO ₂ 0.3	↑ FiO ₂ 0.2	↑ FiO ₂ 0.1	PEEP ↑Trial
22	↑ FiO ₂ 0.3	↑ FiO ₂ 0.3	↑ FiO ₂ 0.3	↑ FiO ₂ 0.3	↑ FiO ₂ 0.3	↑ FiO ₂ 0.2 ↑PEEP 2		↑PEEP 2
20	↑ FiO ₂ 0.3	↑ FiO ₂ 0.3	↑ FiO ₂ 0.3	↑ FiO ₂ 0.2 ↑PEEP 2	↑ FiO ₂ 0.2 ↑PEEP 2	↑ FiO ₂ 0.2 ↑PEEP 2	↑ FiO ₂ 0.1 ↑PEEP 4	↑РЕЕР 4
18	$ \begin{array}{c} \uparrow \operatorname{FiO_2} \\ 0.2 \\ \uparrow \operatorname{PEEP} \\ 2 \end{array} $	↑ FiO ₂ 0.2 ↑PEEP 2		↑ FiO ₂ 0.2 ↑PEEP 2	↑ FiO ₂ 0.1 ↑PEEP 4	↑ FiO ₂ 0.1 ↑PEEP 4	↑ FiO ₂ 0.1 ↑PEEP 4	↑PEEP 4
16		↑ FiO ₂ 0.1 ↑PEEP 4		↑ FiO ₂ 0.1 ↑PEEP 4	↑ FiO ₂ 0.1 ↑PEEP 4	↑ FiO ₂ 0.1 ↑PEEP 4		↑PEEP 4
14	$ \uparrow FiO_2 $ $ 0.2 $ $ \uparrow PEEP $ $ 4 $	↑ FiO ₂ 0.1 ↑PEEP 4		↑ FiO ₂ 0.1 ↑PEEP 4	↑ FiO ₂ 0.1 ↑PEEP 4	↑ FiO ₂ 0.1 ↑PEEP 4		↑PEEP 4
12		↑ FiO ₂ 0.1 ↑PEEP 4		↑ FiO ₂ 0.1 ↑PEEP 4	↑ FiO ₂ 0.1 ↑PEEP 4	↑ FiO ₂ 0.1 ↑PEEP 4		↑PEEP 4
10	↑ FiO ₂ 0.1 ↑PEEP 4	↑ FiO ₂ 0.1 ↑PEEP 4		↑ FiO ₂ 0.1 ↑PEEP 4	↑ FiO ₂ 0.1 ↑PEEP 4	↑ FiO ₂ 0.1 ↑PEEP 4	↑ FiO ₂ 0.1 ↑PEEP 4	↑PEEP 4
8		↑ FiO ₂ 0.1 ↑PEEP 4		↑ FiO ₂ 0.1 ↑PEEP 4	↑ FiO ₂ 0.1 ↑PEEP 4	↑ FiO ₂ 0.1 ↑PEEP 4		↑РЕЕР 4
5	↑ FiO ₂ 0.1 ↑PEEP 5	↑ FiO ₂ 0.1 ↑PEEP 5		↑ FiO ₂ 0.1 ↑PEEP 5	↑ FiO ₂ 0.1 ↑PEEP 5	↑ FiO ₂ 0.1 ↑PEEP 5		↑PEEP 5

PaO₂ 50 to 54 or SpO₂ 85 to 87%

(Use PaO₂ if available, only use SpO₂ if PaO₂ not available)

When PaO_2 or SpO_2 are in this low range, repeated sequential adjustments may be made as guided by the cells in the table until adequate oxygenation with a $SpO_2 \ge 88\%$ is achieved

PEEP	$FiO_2 = .3$	$FiO_2 = .4$	$FiO_2 = .5$	$FiO_2 = .6$	$FiO_2 = .7$	$FiO_2 = .8$	$FiO_2 = .9$	$FiO_2 = 1.0$
24	↑ FiO ₂ 0.1	Consider PEEP Increase Trial						
22	↑ FiO ₂ 0.1	↑ PEEP 2						
20	↑ FiO ₂ 0.1	↑ PEEP 2	↑ PEEP 2	↑ PEEP 2				
18	↑ FiO ₂ 0.1	↑ FiO ₂ 0.1	↑ PEEP 2	↑ PEEP 2				
16	↑ FiO ₂ 0.1	↑ FiO ₂ 0.1	↑ PEEP 2	↑ PEEP 2				
14	↑ FiO ₂ 0.1	↑ PEEP 2	↑ PEEP 2					
12	↑ FiO ₂ 0.1	↑ PEEP 2	↑ PEEP 2					
10	↑ FiO ₂ 0.1	↑ PEEP 2	↑ PEEP 2					
8	↑ FiO ₂ 0.1	↑ PEEP 2	↑ PEEP 2	↑ PEEP 2	↑ PEEP 2	↑ PEEP 2	↑ PEEP 2	↑ PEEP 2
5	↑ FiO ₂ 0.1	↑ PEEP	↑ PEEP 3	↑ PEEP 3	↑ PEEP 3	↑ PEEP 3	↑ PEEP	↑ PEEP 3

$PaO_2 = 55 - 67 \text{ or } SpO_2 88 - 93\%$

(Use PaO₂ if available, only use SpO₂ if PaO₂ not available)

PEEP	$FiO_2 = .3$	$FiO_2 = .4$	$FiO_2 = .5$	$FiO_2 = .6$	$FiO_2 = .7$	$FiO_2 = .8$	$FiO_2 = .9$	$FiO_2 = 1.0$
24	$ \uparrow FiO_2 $ 0.1 $ \downarrow PEEP 2 $	$ \uparrow FiO_2 $ 0.1 $ \downarrow PEEP 2 $			↑ FiO ₂ 0.1 ↓PEEP 2		↓PEEP 2	Maintain
22	$ \uparrow FiO_2 $ 0.1 $ \downarrow PEEP 2 $	$ \uparrow FiO_2 $ 0.1 $ \downarrow PEEP 2 $			↑ FiO ₂ 0.1 ↓PEEP 2	Maintain	Maintain	Maintain
20	$ \uparrow FiO_2 $ 0.1 $ \downarrow PEEP 2 $	$ \uparrow FiO_2 $ 0.1 $ \downarrow PEEP 2 $	Maintain	Maintain	Maintain	Maintain	↑ PEEP 2	$ \downarrow FiO_2 $ 0.1 $ \uparrow PEEP 2 $
18	$ \uparrow FiO_2 $ 0.1 $ \downarrow PEEP 2 $	$ \uparrow FiO_2 $ 0.1 $ \downarrow PEEP 2 $	Maintain	↑ PEEP 2	↑ PEEP 2	↑ PEEP 2	$ \downarrow FiO_2 \\ 0.1 \\ \uparrow PEEP 2 $	$ \downarrow FiO_2 \\ 0.1 \\ \uparrow PEEP 2 $
16	$ \uparrow FiO_2 $ 0.1 $ \downarrow PEEP 2 $	Maintain	Maintain	$ \downarrow FiO_2 $ $ 0.1 $ $ \uparrow PEEP 2 $	↓ FiO ₂ 0.1 ↑PEEP 2	$ \downarrow FiO_2 $ $ 0.1 $ $ \uparrow PEEP 2 $	$ \downarrow FiO_2 $ 0.1 $ \uparrow PEEP 2 $	$\begin{array}{c} \downarrow \text{FiO}_2 \\ 0.1 \\ \uparrow \text{PEEP 2} \end{array}$
14	$ \uparrow FiO_2 $ 0.1 $ \downarrow PEEP 2 $	Maintain	$ \downarrow FiO_2 $ 0.1 $ \uparrow PEEP 2 $	$ \downarrow FiO_2 $ 0.1 $ \uparrow PEEP 2 $	↓ FiO ₂ 0.1 ↑PEEP 2	$ \downarrow FiO_2 $ 0.1 $ \uparrow PEEP 2 $	$ \downarrow FiO_2 $ 0.1 $ \uparrow PEEP 2 $	$ \downarrow FiO_2 $ 0.1 $ \uparrow PEEP 2 $
12	↑ FiO ₂ 0.1 ↓PEEP 2	Maintain	$\begin{array}{c} \downarrow \text{FiO}_2 \\ 0.1 \\ \uparrow \text{PEEP 2} \end{array}$	↓ FiO ₂ 0.1 ↑PEEP 2	↓ FiO ₂ 0.1 ↑PEEP 2	$\begin{array}{c} \downarrow \text{FiO}_2 \\ 0.1 \\ \uparrow \text{PEEP 2} \end{array}$	↓ FiO ₂ 0.1 ↑PEEP 2	$\begin{array}{c} \downarrow \mathrm{FiO_2} \\ 0.1 \\ \uparrow \mathrm{PEEP} \\ 2 \end{array}$
10	↑ FiO ₂ 0.1 ↓PEEP 2	Maintain	$\begin{array}{c} \downarrow \text{FiO}_2 \\ 0.1 \\ \uparrow \text{PEEP 2} \end{array}$	↓ FiO ₂ 0.1 ↑PEEP 2	$\downarrow FiO_2 \ 0.1$ 1. $\uparrow PEEP$ 2	$ \downarrow FiO_2 \\ 0.1 \\ \uparrow PEEP 2 $	↓ FiO ₂ 0.1 ↑PEEP 2	↓ FiO ₂ 0.1 ↑PEEP 2
8	↑ FiO ₂ 0.1	Maintain	$ \downarrow FiO_2 \\ 0.1 \\ \uparrow PEEP 2 $	$ \downarrow FiO_2 \\ 0.1 \\ \uparrow PEEP 2 $	↓ FiO ₂ 0.1 ↑PEEP 2	↓ FiO ₂ 0.1 ↑PEEP 2	\downarrow FiO ₂ 0.1 \uparrow PEEP 2	$ \downarrow FiO_2 \\ 0.1 \\ \uparrow PEEP 2 $
5	Maintain	Maintain	↓ FiO ₂ 0.1 ↑PEEP 3	↓ FiO ₂ 0.1 ↑PEEP 3	↓ FiO ₂ 0.1 ↑PEEP 3	↓ FiO ₂ 0.1 ↑PEEP 3	↓ FiO ₂ 0.1 ↑PEEP 3	↓ FiO ₂ 0.1 ↑PEEP 3

 $PaO_2 > 68 \text{ or } SpO_2 > 93\%$

(Use PaO₂ if available, only use SpO₂ if PaO₂ not available)

PEEP	$FiO_2 = .3$	$FiO_2 = .4$	$FiO_2 = .5$	$FiO_2 = .6$	$FiO_2 = .7$	$FiO_2 = .8$	$FiO_2 = .9$	$FiO_2 = 1.0$
24	↓ PEEP 2	↓ PEEP 2						
22	↓ PEEP 2	↓ PEEP 2	↓ FiO ₂ .1	↓ FiO ₂ .1				
20	↓ PEEP 2	↓ PEEP 2	↓ PEEP 2	↓ FiO ₂ .1				
18	↓ PEEP 2	↓ PEEP 2	↓ PEEP 2	↓ FiO ₂ .1				
16	↓ PEEP 2	↓ PEEP 2	↓ FiO ₂ .1					
14	↓ PEEP 2	↓ PEEP 2	↓ FiO ₂ .1					
12	↓ PEEP 2	↓ PEEP 2	↓ FiO ₂ .1					
10	↓ PEEP 2	↓ PEEP 2	↓ FiO ₂ .1					
8	↓ PEEP 3	↓ PEEP 3	↓ FiO ₂ .1					
5	Maintain	↓ FiO ₂ .1						

$PaO_2 < 50 \text{ or } SpO_2 < 85\%$

(Use PaO₂ if available, only use SpO₂ if PaO₂ not available)

When PaO_2 or SpO_2 are in this low range, repeated sequential adjustments may be made as guided by the cells in the table until adequate oxygenation with a $SpO_2 \ge 88\%$ is achieved

PEEP	FiO ₂ = .3	$FiO_2 = .4$	FiO ₂ = .5	$FiO_2 = .6$	$FiO_2 = .7$	$FiO_2 = .8$	FiO ₂ = .9	$FiO_2 = 1.0$
24	↑ FiO ₂ 0.3	↑ FiO ₂ 0.2	↑ FiO ₂ 0.2	↑ FiO ₂ 0.2	↑ FiO ₂ 0.2	↑ FiO ₂ 0.2	↑ FiO ₂ 0.1	PEEP ↑Trial
22	↑ FiO ₂ 0.3	↑ FiO ₂ 0.2 ↑PEEP 2		↑ FiO ₂ 0.2 ↑PEEP 2	↑ FiO ₂ 0.2 ↑PEEP 2	↑ FiO ₂ 0.2 ↑PEEP 2		↑ PEEP 2
20	↑ FiO ₂ 0.3	↑ FiO ₂ 0.2 ↑PEEP 2	↑ FiO ₂ 0.2 ↑PEEP 2	↑ FiO ₂ 0.2 ↑PEEP 2	↑ FiO ₂ 0.2 ↑PEEP 2	↑ FiO ₂ 0.2 ↑PEEP 2		↑РЕЕР 4
18	↑ FiO ₂ 0.3	↑ FiO ₂ 0.2 ↑PEEP 2	↑ FiO ₂ 0.2 ↑PEEP 2	↑ FiO ₂ 0.2 ↑PEEP 2	↑ FiO ₂ 0.2 ↑PEEP 2	↑ FiO ₂ 0.2 ↑PEEP 2	↑ FiO ₂ 0.1 ↑PEEP 4	↑РЕЕР 4
16	↑ FiO ₂ 0.3	↑ FiO ₂ 0.2 ↑PEEP 2		↑ FiO ₂ 0.2 ↑PEEP 2	↑ FiO ₂ 0.2 ↑PEEP 2	↑ FiO ₂ 0.2 ↑PEEP 2	↑ FiO ₂ 0.1 ↑PEEP 4	↑РЕЕР 4
14	↑ FiO ₂ 0.3	↑ FiO ₂ 0.2 ↑PEEP 2		↑ FiO ₂ 0.2 ↑PEEP 2	↑ FiO ₂ 0.2 ↑PEEP 2	↑ FiO ₂ 0.2 ↑PEEP 2	↑ FiO ₂ 0.1 ↑PEEP 4	↑РЕЕР 4
12	$ \uparrow FiO_2 $ $ 0.2 $ $ \uparrow PEEP $ $ 2 $	↑ FiO ₂ 0.2 ↑PEEP 2	↑ FiO ₂ 0.2 ↑PEEP 2	↑ FiO ₂ 0.2 ↑PEEP 2	↑ FiO ₂ 0.2 ↑PEEP 2	↑ FiO ₂ 0.2 ↑PEEP 2	↑ FiO ₂ 0.1 ↑PEEP 4	↑PEEP 4
10		↑ FiO ₂ 0.2 ↑PEEP 2		↑ FiO ₂ 0.2 ↑PEEP 2	↑ FiO ₂ 0.2 ↑PEEP 2	↑ FiO ₂ 0.2 ↑PEEP 2	↑ FiO ₂ 0.1 ↑PEEP 4	↑PEEP 4
8		↑ FiO ₂ 0.2 ↑PEEP 2		↑ FiO ₂ 0.2 ↑PEEP 2	↑ FiO ₂ 0.2 ↑PEEP 2	↑ FiO ₂ 0.2 ↑PEEP 2		↑PEEP 4
5	↑ FiO ₂ 0.2 ↑PEEP 3	↑ FiO ₂ 0.2 ↑PEEP 3		↑ FiO ₂ 0.2 ↑PEEP 3	↑ FiO ₂ 0.2 ↑PEEP 3	↑ FiO ₂ 0.2 ↑PEEP 3		↑PEEP 5

PaO₂ 50 to 54 or SpO₂ 85 to 87%

(Use PaO₂ if available, only use SpO₂ if PaO₂ not available)

When PaO_2 or SpO_2 are in this low range, repeated sequential adjustments may be made as guided by the cells in the table until adequate oxygenation with a $SpO_2 \ge 88\%$ is achieved

PEEP	$FiO_2 = .3$	$FiO_2 = .4$	$FiO_2 = .5$	$FiO_2 = .6$	$FiO_2 = .7$	$FiO_2 = .8$	$FiO_2 = .9$	$FiO_2 = 1.0$
24	↑ FiO ₂ 0.1	Consider PEEP Increase Trial						
22	↑ FiO ₂	↑ PEEP						
	0.1	0.1	0.1	0.1	0.1	0.1	0.1	2
20	↑ FiO ₂	↑ PEEP						
	0.1	0.1	0.1	0.1	0.1	0.1	0.1	2
18	↑ FiO ₂	↑ PEEP						
	0.1	0.1	0.1	0.1	0.1	0.1	0.1	2
16	↑ FiO ₂	↑ PEEP	↑ PEEP					
	0.1	0.1	0.1	0.1	0.1	0.1	2	2
14	↑ FiO ₂	↑ PEEP	↑ PEEP					
	0.1	0.1	0.1	0.1	0.1	0.1	2	2
12	↑ FiO ₂	↑ FiO ₂	↑ FiO ₂	↑ FiO ₂	↑ PEEP	↑ PEEP	↑ PEEP	↑ PEEP
	0.1	0.1	0.1	0.1	2	2	2	2
10	↑ FiO ₂	↑ FiO ₂	↑ FiO ₂	↑ FiO ₂	↑ PEEP	↑ PEEP	↑ PEEP	↑ PEEP
	0.1	0.1	0.1	0.1	2	2	2	2
8	↑ FiO ₂	↑ FiO ₂	↑ PEEP					
	0.1	0.1	2	2	2	2	2	2
5	↑ FiO ₂ 0.1	↑ PEEP	↑ PEEP 3					

$PaO_2 = 55 - 68 \text{ or } SpO_2 88 - 93\%$

(Use PaO₂ if available, only use SpO₂ if PaO₂ not available)

PEEP	$FiO_2 = .3$	$FiO_2 = .4$	$FiO_2 = .5$	$FiO_2 = .6$	$FiO_2 = .7$	$FiO_2 = .8$	$FiO_2 = .9$	$FiO_2 = 1.0$
24	↑ FiO ₂ 0.1 ↓PEEP 2	↑ FiO ₂ 0.1 ↓PEEP 2	↑ FiO ₂ 0.1 ↓PEEP 2	↑ FiO ₂ 0.1 ↓PEEP 2	↑ FiO ₂ 0.1 ↓PEEP 2	↑ FiO ₂ 0.1 ↓PEEP 2	↑ FiO ₂ 0.1 ↓PEEP 2	Maintain
22	↑ FiO ₂ 0.1 ↓PEEP 2	↑ FiO ₂ 0.1 ↓PEEP 2	↑ FiO ₂ 0.1 ↓PEEP 2	↑ FiO ₂ 0.1 ↓PEEP 2	↑ FiO ₂ 0.1 ↓PEEP 2	↑ FiO ₂ 0.1 ↓PEEP 2	↑ FiO ₂ 0.1 ↓PEEP 2	Maintain
20	↑ FiO ₂ 0.1 ↓PEEP 2	↑ FiO ₂ 0.1 ↓PEEP 2	↑ FiO ₂ 0.1 ↓PEEP 2	↑ FiO ₂ 0.1 ↓PEEP 2	↑ FiO ₂ 0.1 ↓PEEP 2	↑ FiO ₂ 0.1 ↓PEEP 2	↑ FiO ₂ 0.1 ↓PEEP 2	Maintain
18	↑ FiO ₂ 0.1 ↓PEEP 2	↑ FiO ₂ 0.1 ↓PEEP 2	↑ FiO ₂ 0.1 ↓PEEP 2	↑ FiO ₂ 0.1 ↓PEEP 2	↑ FiO ₂ 0.1 ↓PEEP 2	↑ FiO ₂ 0.1 ↓PEEP 2	Maintain	Maintain
16	↑ FiO ₂ 0.1 ↓PEEP 2	↑ FiO ₂ 0.1 ↓PEEP 2	↑ FiO ₂ 0.1 ↓PEEP 2	↑ FiO ₂ 0.1 ↓PEEP 2	↑ FiO ₂ 0.1 ↓PEEP 2	↑ FiO ₂ 0.1 ↓PEEP 2	Maintain	↓ FiO ₂ 0.1 ↑PEEP 2
14	↑ FiO ₂ 0.1 ↓PEEP 2	↑ FiO ₂ 0.1 ↓PEEP 2	↑ FiO ₂ 0.1 ↓PEEP 2	↑ FiO ₂ 0.1 ↓PEEP 2	Maintain	Maintain	Maintain	↓ FiO ₂ 0.1 ↑PEEP 2
12	\uparrow FiO ₂ 0.1 \downarrow PEEP 2	$\uparrow \text{FiO}_2 \text{ 0.1}$ $\downarrow \text{PEEP 2}$	↑ FiO ₂ 0.1 ↓PEEP 2	↑ FiO ₂ 0.1 ↓PEEP 2	Maintain	↓ FiO ₂ 0.1 ↑PEEP 2	↓ FiO ₂ 0.1 ↑PEEP 2	↓ FiO ₂ 0.1 ↑ PEEP 2
10	\uparrow FiO ₂ 0.1 \downarrow PEEP 2	↑ FiO ₂ 0.1 ↓PEEP 2	Maintain	Maintain	Maintain	↓ FiO ₂ 0.1 ↑PEEP 2	↓ FiO ₂ 0.1 ↑PEEP 2	↓ FiO ₂ 0.1 ↑PEEP 2
8	↑ FiO ₂ 0.1 ↓PEEP 3	Maintain	Maintain	↓ FiO ₂ 0.1 ↑PEEP 2				
5	Maintain	Maintain	↓ FiO ₂ 0.1 ↑PEEP 3					

$PaO_2 > 68 \text{ or } SpO_2 > 93\%$

(Use PaO₂ if available, only use SpO₂ if PaO₂ not available)

PEEP	$FiO_2 = .3$	$FiO_2 = .4$	$FiO_2 = .5$	$FiO_2 = .6$	$FiO_2 = .7$	$FiO_2 = .8$	$FiO_2 = .9$	$FiO_2 = 1.0$
24	↓ PEEP 2	↓ PEEP 2						
22	↓ PEEP 2	↓ PEEP 2						
20	↓ PEEP 2	↓ PEEP 2						
18	↓ PEEP 2	↓ PEEP 2	↓ FiO ₂ .1					
16	↓ PEEP 2	↓ PEEP 2	↓ FiO ₂ .1					
14	↓ PEEP 2	↓ PEEP 2	↓ PEEP 2	↓ PEEP 2	↓ PEEP 2	↓ FiO ₂ .1	↓ FiO ₂ .1	↓ FiO ₂ .1
12	↓ PEEP 2	↓ PEEP 2	↓ PEEP 2	↓ PEEP 2	↓ PEEP 2	↓ FiO ₂ .1	↓ FiO ₂ .1	↓ FiO ₂ .1
10	↓ PEEP 2	↓ PEEP 2	↓ PEEP 2	↓ FiO ₂ .1				
8	↓ PEEP 3	↓ PEEP 3	↓ FiO ₂ .1					
5	Maintain	↓ FiO ₂ .1						

$PaO_2 < 55 \text{ or } SpO_2 < 88\%$

(Use PaO₂ if available, only use SpO₂ if PaO₂ not available)

When PaO_2 or SpO_2 are in this low range, repeated sequential adjustments may be made as guided by the cells in the table until adequate oxygenation with a $SpO_2 \ge 92\%$ is achieved

PEEP	FiO ₂ = .3	$FiO_2 = .4$	FiO ₂ = .5	$FiO_2 = .6$	$FiO_2 = .7$	$FiO_2 = .8$	FiO ₂ = .9	$FiO_2 = 1.0$
24	↑ FiO ₂ 0.3	↑ FiO ₂ 0.2	↑ FiO ₂ 0.2	↑ FiO ₂ 0.2	↑ FiO ₂ 0.2	↑ FiO ₂ 0.2	↑ FiO ₂ 0.1	PEEP ↑Trial
22	↑ FiO ₂ 0.3	↑ FiO ₂ 0.2 ↑PEEP 2	↑ FiO ₂ 0.2 ↑PEEP 2	↑ FiO ₂ 0.2 ↑PEEP 2	↑ FiO ₂ 0.2 ↑PEEP 2	↑ FiO ₂ 0.2 ↑PEEP 2		↑ PEEP 2
20	↑ FiO ₂ 0.3	↑ FiO ₂ 0.2 ↑PEEP 2		↑ FiO ₂ 0.2 ↑PEEP 2	↑ FiO ₂ 0.2 ↑PEEP 2	↑ FiO ₂ 0.2 ↑PEEP 2	↑ FiO ₂ 0.1 ↑PEEP 4	↑РЕЕР 4
18	↑ FiO ₂ 0.3	↑ FiO ₂ 0.2 ↑PEEP 2	↑ FiO ₂ 0.2 ↑PEEP 2	↑ FiO ₂ 0.2 ↑PEEP 2	↑ FiO ₂ 0.2 ↑PEEP 2	↑ FiO ₂ 0.2 ↑PEEP 2	↑ FiO ₂ 0.1 ↑PEEP 4	↑РЕЕР 4
16	↑ FiO ₂ 0.3	↑ FiO ₂ 0.2 ↑PEEP 2		↑ FiO ₂ 0.2 ↑PEEP 2	↑ FiO ₂ 0.2 ↑PEEP 2	↑ FiO ₂ 0.2 ↑PEEP 2	↑ FiO ₂ 0.1 ↑PEEP 4	↑РЕЕР 4
14	↑ FiO ₂ 0.3	↑ FiO ₂ 0.2 ↑PEEP 2		↑ FiO ₂ 0.2 ↑PEEP 2	↑ FiO ₂ 0.2 ↑PEEP 2	↑ FiO ₂ 0.2 ↑PEEP 2	↑ FiO ₂ 0.1 ↑PEEP 4	↑PEEP 4
12	$ \uparrow FiO_2 $ $ 0.2 $ $ \uparrow PEEP $ $ 2 $	↑ FiO ₂ 0.2 ↑PEEP 2	↑ FiO ₂ 0.2 ↑PEEP 2	↑ FiO ₂ 0.2 ↑PEEP 2	↑ FiO ₂ 0.2 ↑PEEP 2	↑ FiO ₂ 0.2 ↑PEEP 2	↑ FiO ₂ 0.1 ↑PEEP 4	↑РЕЕР 4
10		↑ FiO ₂ 0.2 ↑PEEP 2	↑ FiO ₂ 0.2 ↑PEEP 2	↑ FiO ₂ 0.2 ↑PEEP 2	↑ FiO ₂ 0.2 ↑PEEP 2	↑ FiO ₂ 0.2 ↑PEEP 2		↑РЕЕР 4
8		↑ FiO ₂ 0.2 ↑PEEP 2	↑ FiO ₂ 0.2 ↑PEEP 2	↑ FiO ₂ 0.2 ↑PEEP 2	↑ FiO ₂ 0.2 ↑PEEP 2	↑ FiO ₂ 0.2 ↑PEEP 2	↑ FiO ₂ 0.1 ↑PEEP 4	↑РЕЕР 4
5	↑ FiO ₂ 0.2 ↑PEEP 3	↑ FiO ₂ 0.2 ↑PEEP 3		↑ FiO ₂ 0.2 ↑PEEP 3	↑ FiO ₂ 0.2 ↑PEEP 3	↑ FiO ₂ 0.2 ↑PEEP 3		↑РЕЕР 5

PaO₂ 55 to 67 or SpO₂ 88 to 92%

(Use PaO₂ if available, only use SpO₂ if PaO₂ not available)

When PaO_2 or SpO_2 are in this low range, repeated sequential adjustments may be made as guided by the cells in the table until adequate oxygenation with a $SpO_2 \ge 92\%$ is achieved

PEEP	$FiO_2 = .3$	$FiO_2 = .4$	$FiO_2 = .5$	$FiO_2 = .6$	$FiO_2 = .7$	$FiO_2 = .8$	$FiO_2 = .9$	$FiO_2 = 1.0$
24	↑ FiO ₂ 0.1	Consider PEEP Increase Trial						
22	↑ FiO ₂	↑ PEEP						
	0.1	0.1	0.1	0.1	0.1	0.1	0.1	2
20	↑ FiO ₂	↑ PEEP						
	0.1	0.1	0.1	0.1	0.1	0.1	0.1	2
18	↑ FiO ₂	↑ PEEP						
	0.1	0.1	0.1	0.1	0.1	0.1	0.1	2
16	↑ FiO ₂	↑ PEEP	↑ PEEP					
